# Statistical Analysis

#### Recruitment

Previous exercise research suggests that the difference in response of matched pairs is normally distributed with a standard deviation of 0.86. If the true difference of the mean response of matched pairs is 0.75, we will need to complete 12 experimental trials for each condition to be able to reject the null hypothesis that this response difference is zero with a power of 0.8. The Type I error probability associated with this test of the null hypothesis is 0.05.

#### Interventions

A repeated measures two-way ANOVA (Time x condition) will be used for the dependent variables. If the F-ratio values are found to be significant, a Fisher's Least Significant Difference post hoc analysis will be conducted. A type I error probability of < 5% will be considered significant (p< 0.05). All data will be analyzed using a combination of Microsoft Excel and the Statistical Package for the Social Sciences (SPSS).

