#### **Abstract**

The purpose of this study is to examine the human thermoregulatory impact of applying a commercially available menthol gel (BioFreeze) to the skin prior to moderate intensity walking under heated conditions. Eligible participants will be aged 19-45 years, have no previously known adverse reactions to menthol (active ingredient in BioFreeze) based upon a self-report, no adverse reactions to BioFreeze as determined through gel application to a small forearm area, and cleared for physical activity via the 2022 Physical Activity Readiness Questionnaire (PARQ). There will be a total of 3 experimental visits to the laboratory. Visit 1 will test for adverse BioFreeze reaction by applying a small amount of gel to the forearm (~2 x 2 in). Anthropometric and body composition data will also be collected at this time. Visits 2 and 3 will consist of 30 min of treadmill walking at a moderate pace (3.5 mph, 5% grade) under hot conditions (38°C, 60%RH). Visits 2 and 3 will be randomized and counterbalanced for BioFreeze or a hypoallergenic gel (control) application. Gels will be applied to areas commonly exposed during outdoor activity in warm conditions (shoulder to wrist, mid-thigh to ankle). Accordingly, participants will wear shorts and a tank top shirt during exercise. Core temperature, skin temperature, galvanic skin response, laser doppler blood flow, and heart rate will be continuously recorded throughout the exercise bout via an integrated analog to digital converter. Sweat will be collected during exercise using commercially available absorbent patches. Thermal sensation will be assessed throughout exercise via the ASHRAE thermal sensation likert scale (cold to hot). Lastly, nude body weight will be recorded pre and post exercise for sweat rate determination. The BioFreeze and control trials will be separated by a 7 to 14 day washout period.

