#### Research Plan

Three experimental visits to the laboratory will be conducted. All visits will take place at the University of Nebraska at Omaha, Exercise Physiology Laboratory. Visit 1 will consist of the physical activity readiness questionnaire (PARQ), adverse reaction to BioFreeze, and body composition (hydrostatic weigh, bioelectrical impedance). Visits 2 and 3 will be separated by 7-14 days, randomized, and counterbalanced for experimental (BioFreeze) and control (hypoallergenic cream) trials. Both the experimental and control visits will follow the same protocol.

Participants will arrive following an overnight fast state while also refraining from strenuous activity, alcohol consumption, tobacco use, and recreational drugs for the previous 24-hour period. During these visit researchers will apply BioFreeze using a gloved hand from shoulder to wrist and mid-thigh to ankle (areas outside of the clothing). A hypoallergenic cream will be applied during the control visit.

Exercise will consist of 30 min of moderate intensity treadmill walking (3.5 mph at 5% grade) within a heated temperature/humidity-controlled chamber (38°C, 60% relative humidity).

Participants will be weighed before, and after completion of the exercise calculate sweat rate. Prior to the exercise session, participants will sit for 5 min in an ambient room temperature environment as a baseline. During baseline and during the exercise core temperature, skin temperature, laser doppler blood flow, galvanic skin response, and heart rate will be collected continuously. Sweat patches will be adhered to the forehead during exercise at minute 10 for collection of sweat composition over the next 10-20 minutes.

Thermal perception using the ASHRAE scale (cold to hot) will be assessed pre and during exercise.

### VISIT 1

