Following instrumentation, subjects will sit for 5 minutes as a baseline in a temperate environment. Immediately after, a researcher with gloved hands will topically apply BioFreeze or the control hypoallergenic cream from the shoulder to wrist and mid-thigh to ankle. Subjects will then enter the heat chamber (38°C, 60% relative humidity) and immediately begin a 30-minute walk on a treadmill (3.5 mph, 5% grade). Subjects will be intermittently asked to hold their arm steady for laser doppler flow collection (10, 20, 30 minutes). Subjects will also briefly pause at minute 10 in order to adhere an absorbent patch to their forehead for sweat collection over the following 10-20 minutes. Thermal perception using the ASHRAE scale (cold to hot) will be assessed pre and during exercise. After 30 minutes of walking, subjects will exit the chamber for removal of all skin and finger sensors. Subjects will then reenter the private room, remove their own rectal thermistor with gloved hands, and then a final nude body weight will be recorded after toweling off.

The rectal thermistor will measure core temperature. The heart rate monitor will measure the beats of the heart. Skin thermistors will measure the temperature of the skin surfaces. Laser doppler flow measure the relative units of blood flow velocity.

Galvanic skin response measures skin conductivity changes as individuals begin to sweat. Sweat is collected for assessment of sweat composition. Thermal perception is assessed for individual perception surrounding the temperature of the ambient environment. Nude body weight is measured to calculate sweat rate.

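### No primary outcome or deciding contrast is named: about eight outcome domains are each tested at p<0.05, and the power inputs belong to no stated outcome

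*Combined protocol and SAP*

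**What the plan says.** The statistical section has two short paragraphs.

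- **Interventions.** "A repeated measures two-way ANOVA (Time x condition) will be used for the dependent variables". The threshold is p<0.05. Fisher's LSD comparisons follow "If the F-ratio values are found to be significant"; the paragraph does not say which F-ratio (time, condition or their interaction) is meant. No dependent variable is listed or ranked.
- **Recruitment.** The size rests on earlier exercise research in which "the difference in response of matched pairs is normally distributed with a standard deviation of 0.86". With a true mean difference of 0.75, 12 trials per condition are said to be enough to "reject the null hypothesis that this response difference is zero with a power of 0.8", at a Type I error of 0.05. The response is not identified and sidedness is not stated.

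The outcomes are described elsewhere. The Abstract states: "Core temperature, skin temperature, galvanic skin response, laser doppler blood flow, and heart rate will be continuously recorded throughout the exercise bout". The Research Plan adds: "Thermal perception using the ASHRAE scale (cold to hot) will be assessed pre and during exercise". Under Visits 2 and 3, participants pause at minute 10 for staff to "adhere an absorbent patch to their forehead for sweat collection over the following 10-20 minutes", and "Nude body weight is measured to calculate sweat rate". That makes eight domains: core temperature, skin temperature, heart rate, galvanic skin response, laser Doppler flow, thermal sensation, sweat rate and sweat composition. Purpose and Rationale gives an aim broad enough to cover all of them. Participants plans for 12 to 15 people to complete.

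**The concern.** The plan does not tell a reader which result answers the study question. Eight domains can each produce a p-value below 0.05, and within most of them two F-ratios involve condition. If whichever result reaches significance is reported as the effect of BioFreeze, the chance of reporting an effect when there is none is well above 5%.

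The LSD step does not remove this. It limits pairwise comparisons inside one ANOVA and has no bearing on the other outcomes. Because the F-ratio that opens it is unnamed, a significant time effect, which is to be expected over 30 minutes of walking at 38°C, could be taken as enough to start BioFreeze-versus-control comparisons.

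The sample-size statement does not fill the gap. With no outcome or unit attached, nobody can judge whether 0.75 is plausible or important, or which comparison 12 to 15 completers were chosen to detect.

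**Working it through.** **1. The plan's own figure.** Inputs from Recruitment: mean paired difference 0.75, SD of differences 0.86, alpha 0.05. Two-sided testing is assumed. The method is a paired t-test with the noncentral t distribution, n−1 degrees of freedom and noncentrality (0.75/0.86)×√n, where 0.75/0.86 = 0.872.

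| Completers | Noncentrality | Power |
|---|---|---|
| 12 | 0.872×√12 = 3.02 | 0.785 |
| 13 | 0.872×√13 = 3.14 | 0.823 |
| 14 | 0.872×√14 = 3.26 | 0.854 |
| 15 | 0.872×√15 = 3.38 | 0.881 |

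The stated 12 is therefore nearly right: power is 1.5 points below 0.80, and 13 completers pass it. The arithmetic is not the main problem.

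**2. What the power inputs could refer to.** With two conditions, the condition F-ratio equals the squared paired t on time-averaged values. On simulated data with n=12, both were 0.6530. With two time points, the interaction F-ratio equals the squared paired t on change scores (both 1.8714). A paired-difference calculation could therefore describe either term. The documents do not say which, or for which outcome.

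**3. Across outcomes.** Assume no true effect, one 5% test per domain, and any p<0.05 read as a BioFreeze effect. For independent outcomes the chance of at least one is 1 − 0.95^8 = 1 − 0.663 = 0.337. For correlated outcomes: 200,000 simulated studies, n=12 pairs, normal differences with equal correlation between outcomes, and a two-sided paired t-test on each.

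| Assumed correlation | Chance of at least one p<0.05 |
|---|---|
| 0 | 0.338 |
| 0.3 | 0.306 |
| 0.5 | 0.262 |
| 0.7 | 0.202 |
| 0.9 | 0.126 |

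Even at 0.9 this is about 2.5 times the nominal 5% (0.126/0.05). The count of eight would rise if the three skin sites or several sweat analytes were tested separately.

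**4. Within one outcome.** If either the condition or the Time x condition F-ratio may count, the chance under sphericity is 1 − 0.95² = 0.0975; simulation with n=12 and four assumed time points gave 0.097. The plan states no sphericity correction. With assumed serially correlated differences and no correction, the interaction test alone rejects in 6.7% to 7.6% of null studies, and either term in about 11%.

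**5. Fit of the model.** Sweat rate is calculated from weights before and after exercise, and one patch is worn per visit. Each gives one value per visit, so neither has a time factor. The two weights could be entered as a 2×2 layout, in which the interaction matches the difference in weight loss. The condition main effect in that layout compares average body weight between visits and does not measure sweating. The plan does not say that weight replaces sweat rate as the dependent variable.

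**The case against.** The strongest reply is that the study sets out to examine an effect and states no rule that one significant outcome means success. Separate conclusions about core temperature, sweating and perception do not automatically call for familywise control. This stands as a limit on the numbers: the 13% to 34% applies only if any p<0.05 is read as a BioFreeze effect. It does not remove the gap, because the plan states a null hypothesis, a power and a significance threshold without saying which outcome they serve, and it does not call itself exploratory.

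Four stronger readings are tempting and are not supported:

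- *That 34% is this study's error rate.* It is the upper end for one test per domain under non-negative correlation, and the documents give no correlations.
- *That nothing was prespecified.* The paired design, model factors, threshold and power inputs are all stated. What is missing from the text reviewed is a primary outcome and a deciding contrast. Front matter withheld from review could not be checked.
- *That the sample size is wrong, or that a paired calculation cannot serve an ANOVA.* Twelve is close to right at the stated inputs, and a paired difference can correspond to a condition-related F-ratio.
- *That the ANOVA fits none of the outcomes.* The misfit as written concerns sweat rate and patch composition only.

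**Conclusion.** The point holds and should be fixed. The reviewed text names no primary outcome and no deciding contrast, applies an unadjusted 5% threshold to about eight domains, and leaves 0.75 and 0.86 without an outcome, unit or time point. The cost of reading any significant result as the effect is a false-positive chance of about 13% to 34%, with one test per domain, n=12, normal differences and equal correlations assumed between 0.9 and 0. Letting either condition-related F-ratio count within one outcome gives about 9.75% under sphericity, and more without a correction. The shortfall in power at 12 completers (78.5% against 80%, two-sided assumed) is minor.

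**What to change.** Make these changes before any data are seen.

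**In Interventions:**
- Name one primary outcome, which is the sponsor's choice.
- Name one condition-related contrast, tested at two-sided 5%: either a paired BioFreeze-minus-control difference at a stated time or one named ANOVA term. If that term is the interaction with more than two time points, state how sphericity is handled.
- List all other outcomes as exploratory, reported with estimates and 95% confidence intervals.
- Specify a paired comparison for both sweat rate and patch sweat composition.

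**In Recruitment:**
- State which outcome, unit and time point 0.75 and 0.86 refer to.
- If they belong to the primary contrast, restate power as about 78.5% with 12 completers or 82% with 13, which is inside the planned 12 to 15.
- If they do not, recompute and restate power from the primary's own difference and SD.

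**Cost.** Only wording changes if the inputs belong to the named primary. Otherwise the sample size must be rechecked and may change. The other outcomes could no longer support confirmatory claims, and the stated power becomes slightly less favourable.
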